8. BIOSPECIMEN STUDIES AND PROCEDURES

Correlative blood and fresh tissue studies will be analyzed at Indiana University. Please refer to the Correlative Laboratory Manual (CLM) for all sample collection, processing, labeling, and shipping instructions.

8.1 Tissue

Missed biopsies will not be considered protocol deviations for the purposes of this study.

8.1.1 Tissue at Screening

Archival tissue from a metastatic lesion or nephrectomy (metastatic lesion preferred) is required if available and will be obtained at screening after eligibility is reviewed. If archival tissue is unavailable, patients will be given the option to consent to a biopsy during the screening phase prior to treatment. Representative formalin-fixed paraffin-embedded (FFPE) tumor specimens in paraffin blocks (blocks are preferred) or at least 4 unstained slides, with an associated pathology report, for central testing of tumor PD-L1 expression.

- Tumor tissue suitable for PD-L1 expression testing should be of good quality based on total and viable tumor content. Fine needle aspiration, brushing, cell pellet from pleural effusion, bone metastases, and lavage samples are not acceptable. Tumor tissue from bone metastases is not evaluable for PD-L1 expression and is therefore not acceptable. For core-needle biopsy specimens, at least three cores should be submitted for evaluation.
- Acceptable samples include core needle biopsies for deep tumor tissue (minimum of three cores) or excisional, incisional, punch, or forceps biopsies for cutaneous, subcutaneous, or mucosal lesions.

8.1.2 Fresh Tissue Cycle 2 Day 1

All subjects with accessible tumor will be given the option to consent to a second, optional biopsy during Cycle 2 on Day 1 (± 7 days). Screening and Cycle 2 Day 1 tumor biopsy samples for gene expression analysis will be collected from patients who consent and who have accessible tumor per institutional procedures. The biopsy sample will be split into two portions: one (1) portion will be placed in RNAlaterTM and one (1) portion will be placed in 10% formalin solution.

The Cycle 2 Day 1 samples will be collected ~ 2 hours following the most recent dose of entinostat. To ensure that these samples are obtained at the correct time, patients are urged to take their entinostat dose in the clinic on the day of on-treatment sample collection. The time of the entinostat dose and the time of sample collection must be recorded.

Biomarker assays will be done by IHC to examine:

- PDL-1/2
- T effector cells
- Tregs
- MDSCs
- M1/M2 macrophages

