3: Thyroid function to be checked at screening, Cycle 2 Day 1, Cycle 4 Day 1, then every 3rd cycle thereafter starting with Cycle 6. More frequent testing is at the discretion of the site investigator. TSH will be obtained. T4 and T3 including free versus total testing is at the discretion of the site investigator.

4: For women of childbearing potential (WOCBP): serum pregnancy test during screening and a urine pregnancy test within 3 days prior to first dose of study drugs. If the screening serum test was done within 3 days prior to receiving the first dose of study drugs, a urine test is not required.

5: Tumor response assessment will be performed at screening, prior to Cycle 3 Day 1 then prior to Cycle 5 (±7); Tumor imaging to be performed every 8-12 weeks after Cycle 5 based on investigator discretion. Tumor imaging to be done at treatment discontinuation at discretion of investigator. Baseline bone scan will be obtained if there is any suspicion of metastatic bone involvement. If bone scan is positive at baseline, it will be included with subsequent tumor response assessments as noted above at the discretion of the treating physician. MRI of brain should be performed at screening only to evaluate for the presence of brain metastases. Additional imaging of the brain will be at the discretion of the treating physician. Tumor imaging modality used should be consistent throughout trial.

6: Archival tissue from a metastatic lesion or nephrectomy (metastatic lesion preferred) is required if available and will be obtained at screening. If archival tissue is unavailable, patients will be given the option to consent to a biopsy during the screening phase prior to Cycle 1 Day 1 treatment. All subjects with accessible tumor will be given the option to consent to a second optional biopsy on Cycle 2 Day 1. The Cycle 2 Day 1 samples will be collected ~2 hours following the most recent dose of entinostat. To ensure that these samples are obtained at the correct time, patients are urged to take their entinostat dose in the clinic on the day of on-treatment sample collection. The time of the entinostat dose and the time of sample collection must be recorded.

7: Serial blood samples for PBMCs and plasma, serum will be collected prior to treatment Cycle 1 Day 1, Cycle 2 Day 1, Cycle 4 Day 1, and then every 2nd cycle thereafter starting with Cycle 6.

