12.7.3 Analysis Plans for Exploratory Objectives

Quantitative analysis of correlative endpoints will be characterized by their mean and corresponding 95% confidence interval by time point. Changes over time in PD-L1/L2 expression levels in tumor and blood, microRNA, and immune markers (see Section 8 for details) will be analyzed with paired t-tests. Correlations with clinical outcomes will be examined using logistic and Cox regression models. Similar

to Section 12.7.1, the analysis will be first done for all evaluable and eligible patients, and then stratified for their previous treatment (nivolumab plus ipilimumab vs nivolumab alone) in the analysis using the logistic and Cox regression models.

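### The paired t-test on tumour markers has no defined baseline specimen, so archival tissue that may predate checkpoint therapy can be tested as if it were a pre-treatment sample

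*Combined protocol and SAP*

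**What the plan says.** Section 8.1.1 sets the default screening specimen: "Archival tissue from a metastatic lesion or nephrectomy (metastatic lesion preferred) is required if available". It puts no limit on the age of the tissue or on its timing relative to earlier therapy. A fresh screening sample is conditional: "If archival tissue is unavailable, patients will be given the option to consent to a biopsy during the screening phase prior to treatment". Footnote 6 of the study calendar (section 7) repeats that condition. The screening FFPE material is submitted "with an associated pathology report, for central testing of tumor PD-L1 expression".

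Section 8.1.2 describes the on-treatment specimen: "All subjects with accessible tumor will be given the option to consent to a second, optional biopsy during Cycle 2 on Day 1", with a window of 7 days either side. It then says: "Screening and Cycle 2 Day 1 tumor biopsy samples for gene expression analysis will be collected from patients who consent", provided the tumour is accessible. The IHC list in that section covers PD-L1/2, T effector cells, Tregs, MDSCs and macrophages.

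Section 12.7.3 assigns paired t-tests to "Changes over time in PD-L1/L2 expression levels in tumor and blood, microRNA, and immune markers". It does not say which tumour specimen is the baseline, and it does not separate or adjust for specimen type, date, site or intervening therapy.

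Under inclusion criterion 6 in section 3.1, every patient has progressed on nivolumab plus ipilimumab or on nivolumab alone before entry. Criterion 9 also allows other earlier cancer treatment.

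**The concern.** A paired test of change on treatment needs a first sample that shows the tumour as it was when study treatment began. A nephrectomy or older metastasis block taken before checkpoint therapy does not. The interval between it and Cycle 2 Day 1 can include the earlier nivolumab or ipilimumab, progression on it, other therapy and simple passage of time, and the two samples may come from different lesions. Any of these can move a marker such as PD-L1 while the study regimen does nothing.

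The hypothesis in section 1.4 is about restoring an immune response in patients who have already progressed on checkpoint inhibitors, so the relevant baseline is tissue taken after that progression. If archival and fresh baselines go into one test, a significant result cannot be attributed to the study regimen. A null result is no easier to read, because the drift could also run against a real effect.

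**Working it through.** **The plan's own figures.** The documents give no calculation for the paired t-test. Their only design calculation is the Simon two-stage design in section 12.3, and it reproduces. At a 5% response rate, the probability of at most 1 response in 21 is 0.95^21 + 21 × 0.05 × 0.95^20 = 0.717, and the expected sample size is 21 + (1 − 0.7170) × 20 = 26.66. Nothing below affects it.

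**Which baseline each patient has, reading the sections together.**

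- Archival tissue exists: sections 7 (footnote 6) and 8.1.1 clearly provide only that sample before treatment. It may predate checkpoint progression or follow it; the plan does not say.
- No archival tissue, and the patient consents to a screening biopsy: a fresh baseline, taken after progression.
- No archival tissue and no consent: no tumour pair.

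Section 12.7.3 draws no line between the first two groups, so both enter the same test.

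**Illustration of size.** None of these inputs is a document figure: a two-sided 5% level, n pairs, zero study effect, and a drift of d standard deviations of the within-pair difference in pairs with a drifting archival baseline. Six pairs would be one complete lead-in dose cohort, and 18 is the lead-in maximum in section 12.3. Both are generous, because the Cycle 2 biopsy is optional.

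If all pairs are archival, the test statistic follows a noncentral t distribution with n − 1 degrees of freedom and noncentrality d√n. The rejection probability is P(|T| > t critical). For n = 6 the noncentrality is 0.5 × √6 = 1.22 at d = 0.5, and 1.0 × √6 = 2.45 at d = 1.0. If each pair has a 50% chance of being archival, the rate comes from 40,000 simulated trials.

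| Pairs | Drift (SD) | All archival | Half archival |
|---|---|---|---|
| 6 | 0.25 | 8.0% | 5.5% |
| 6 | 0.5 | 17.1% | 7.9% |
| 6 | 1.0 | 50.7% | 14.5% |
| 12 | 0.5 | 35.3% | 12.2% |
| 12 | 1.0 | 88.3% | 29.8% |
| 18 | 0.5 | 51.6% | 16.3% |
| 18 | 1.0 | 97.9% | 43.3% |

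With no drift the rate is the nominal 5%. More pairs make the problem worse, because the test becomes more certain of a difference that is not a treatment effect.

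**The case against.** The strongest reply is that section 12.7.3 never says archival tissue is the baseline. Several places suggest separate archival and fresh workflows. Section 8 opens by assigning blood and fresh tissue studies to the university laboratory. The Treg, MDSC and macrophage list sits under the fresh-tissue heading. Section 8.1.2 pairs screening with Cycle 2 biopsies and calls the latter a second biopsy. The calendar has its own row for an optional fresh biopsy, marked at both screening and Cycle 2. The Correlative Laboratory Manual, which is not among the documents, may settle the pairing.

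Much of this stands, and it rules out three readings a reader might reach:

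- That most patients have an archival baseline. No availability rate is given.
- That the archival sample always predates checkpoint therapy. Section 8.1.1 prefers a metastatic lesion, and tissue taken after progression would qualify.
- That the Treg and MDSC comparisons are affected to the same degree as PD-L1. Only PD-L1 is expressly tied to the screening FFPE tissue.

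It does not remove the point. Section 8.1.1 and footnote 6 still make the fresh screening biopsy conditional on having no archival tissue. The sentence in 8.1.2 about paired biopsies concerns gene expression. On any reading, 12.7.3 does not confine the test to fresh pairs.

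It is also fair to say that the remedy buys limited insight. Nivolumab and ipilimumab are given with entinostat from Cycle 1 Day 1, and no rule requires the same lesion to be sampled twice. Even clean pairs show the effect of the three-drug regimen, possibly across lesions.

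**Conclusion.** The point holds as a minor one. Sections 8.1.1 and 8.1.2 do not agree on who has a fresh screening sample. Because 12.7.3 leaves the baseline undefined, following the plan as written can pool pairs whose change is not attributable to the study regimen. The argument is clearest for tumour PD-L1.

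The size is unknown. The 17% and 51% figures might be read as this trial's false-positive rate; they are not. They assume 6 pairs, a drift of 0.5 or 1.0 SD and an entirely archival set, and they fall to about 8% and 15% if half the pairs are archival. The documents fix none of these inputs, nor the direction of the drift.

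The consequence is limited. The analysis is exploratory, and accrual halts after the safety lead-in. Blood markers have their own sample before treatment on Cycle 1 Day 1, and the objective response rate is untouched.

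**What to change.** In section 12.7.3:

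1. Define the tumour baseline as tissue taken after progression on the earlier checkpoint therapy and before Cycle 1 Day 1. Recent archival tissue that meets this counts.
2. Limit the paired t-test to pairs with such a baseline.
3. Show the remaining archival-to-Cycle 2 pairs separately and descriptively, with tissue date, site and intervening therapy, and no p-value.
4. State that any change is read as an effect of the combination, not of entinostat alone.

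Sections 8.1.1 and 8.1.2 and calendar footnote 6 should also be reconciled on who provides a fresh screening sample.

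The cost is wording. A pathology report already accompanies the screening specimen, and the calendar already requires earlier anti-cancer treatment to be documented. Section 12 allows analysis changes without a protocol amendment unless a significant feature changes, provided they are documented in the final study report. The real downside is that few pairs, possibly none, may remain to test. In that case the tumour results should be presented descriptively.

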8.2 Peripheral Blood Samples

8.2.1 Whole Blood

Serial blood samples for PBMCs and plasma, serum will be collected during prior to treatment C1D1, Cycle 2 Day 1, Cycle 4 Day 1, and then every 2nd cycle thereafter starting with Cycle 6. Blood samples should be collected prior to treatment administration whenever possible. Biomarker assays will be done to examine:

- CD45 cells
- Effector CD4 T cells
- Effector CD8 T cells
- FoxP3+ CD4+ Regulatory T cells (Tregs)
- CD11b+ CD14+ HLA-DR low/neg MDSCs
- Circulating microRNAs

8.3 Samples for future studies

Subject consent will be obtained for additional samples collected for future unspecified cancer related research. Hoosier Cancer Research Network will manage the banked samples. Samples will be banked indefinitely in the Hoosier Cancer Research Network Biorepository.

This includes:

- Whole blood: Whole blood will be collected prior to treatment on Cycle 1 Day 1.
- Pre- and Post-treatment plasma: Whole blood for plasma will be collected prior to treatment on Cycle 1 Day 1 and at the 30-day Safety Follow-up visit.
- Pre- and Post-treatment serum: Whole blood for serum will be collected prior to treatment on Cycle 1 Day 1 and at the 30-day Safety Follow-up visit.
- Unstained slides: Unstained slides will be obtained from the subject's archived formalin fixed paraffin embedded tumor sample.

Please refer to the Correlative Laboratory Manual (CLM) for all sample collection, processing, labeling, and shipping instructions.

8.4 Storage of Biospecimens

Any specimens remaining (leftover) once protocol described biospecimen-based studies are complete will be stored for future unspecified cancer related research. Permission for storage of leftover samples will be obtained from subjects during informed consent.

8.5 Confidentiality of Biospecimens

Samples that are collected will be identified by a subject's sequence ID assigned at the time of registration to the trial. Any material issued to collaborating researchers will be anonymized and only identified by the subject's study number.

9. CRITERIA FOR DISEASE EVALUATION

Response assessments will be made both using the Immune Related Response Criteria (irRC) and using RECIST v1.1, allowing additional comparisons among these criteria for disease response assessment. The same measurable and non-measurable lesions will be followed by both RECIST v1.1 & irRC. Disease progression will be determined using RECIST 1.1 criteria.

9.1 Measurable Disease

Measurable disease is defined as the presence of at least one measurable lesion. Measurable lesions are defined as those that can be accurately measured in at least one dimension (longest diameter to be recorded) as ≥ 20 mm by chest x-ray, as ≥ 10 mm with CT scan, or ≥ 10 mm with calipers by clinical exam. All tumor measurements must be recorded in millimeters (or decimal fractions of centimeters).

9.1.1 Malignant Lymph Nodes

To be considered pathologically enlarged and measurable, a lymph node must be ≥ 15 mm in short axis when assessed by CT scan (CT scan slice thickness recommended to be no greater than 5 mm). At baseline and in follow-up, only the short axis will be measured and followed.

9.2 Non-measurable Lesions

All other lesions (or sites of disease), including small lesions (longest diameter <10 mm or pathological lymph nodes with ≥ 10 to <15 mm short axis), are considered non-measurable disease. Bone lesions, leptomeningeal disease, ascites, pleural/pericardial effusions, lymphangitis cutis/pulmonitis, inflammatory breast disease, and abdominal masses (not followed by CT or MRI), are considered as non-measurable.

NOTE: Cystic lesions that meet the criteria for radiographically defined simple cysts should not be considered as malignant lesions (neither measurable nor non-measurable) since they are, by definition, simple cysts. ‘Cystic lesions’ thought to represent cystic metastases can be considered as measurable lesions, if they meet the definition of measurability described above. However, if non-cystic lesions are present in the same subject, these are preferred for selection as target lesions.

9.3 Target Lesions

All measurable lesions up to a maximum of 2 lesions per organ and 5 lesions in total, representative of all involved organs, should be identified as target lesions and recorded and measured at baseline. Target lesions should be selected on the basis of their size (lesions with the longest diameter), be representative of all involved organs, but in addition should be those that lend themselves to reproducible repeated measurements. It may be the case that, on occasion, the largest lesion does not lend itself to reproducible measurement in which circumstance the next largest lesion which can be measured reproducibly should be selected. A sum of the diameters (longest for non-nodal lesions, short axis for nodal lesions) for all target lesions will be calculated and reported as the baseline sum diameters. If lymph nodes are to be included in the sum, then only the short axis is added into the sum. The baseline sum diameters will be used as reference to further characterize any objective tumor regression in the measurable dimension of the disease.

9.4 Non-target Lesions

All other lesions (or sites of disease) including any measurable lesions over and above the 5 target lesions should be identified as non-target lesions and should also be recorded at baseline. Measurements of these lesions are not required, but the presence, absence, or in rare cases unequivocal progression of each should be noted throughout follow-up.

9.5 Evaluation of Target Lesions

Complete Response (CR)	Disappearance of all target lesions. Any pathological lymph nodes (whether target or non-target) must have reduction in short axis to <10 mm.
Partial Response (PR)	At least a 30% decrease in the sum of the diameters of target lesions, taking as reference the baseline sum diameters
Progressive Disease (PD)	At least a 20% increase in the sum of the diameters of target lesions, taking as reference the smallest sum on study (this includes the baseline sum if that is the smallest on study). In addition to the relative increase of 20%, the sum must also demonstrate an absolute increase of at least 5 mm. (Note: the appearance of one or more new lesions is also considered progressions).
Stable Disease (SD)	Neither sufficient shrinkage to qualify for PR nor sufficient increase to qualify for PD, taking as reference the smallest sum diameters while on study

9.6 Evaluation of Non-Target Lesions

Complete Response (CR)	Disappearance of all non-target lesions and normalization of tumor marker level. All lymph nodes must be non-pathological in size (<10 mm short axis) Note: If tumor markers are initially above the upper normal limit, they must normalize for a subject to be considered in complete clinical response.
Non-CR/ Non-PD	Persistence of one or more non-target lesion(s) and/or maintenance of tumor marker level above the normal limits
Progressive Disease (PD)	Appearance of one or more new lesions and/or unequivocal progression of existing non-target lesions. Unequivocal progression should not normally trump target lesion status. It must be representative of overall disease status change, not a single lesion increase.

Although a clear progression of “non-target” lesions only is exceptional, the opinion of the site investigator should prevail in such circumstances, and the progression status should be confirmed at a later time by the sponsor investigator.

9.7 Evaluation of Best Overall Response

Target Lesions	Non-Target Lesions	New Lesions	Overall Response
CR	CR	No	CR
CR	Non-CR/ Non-PD	No	PR
CR	Not evaluated	No	PR
PR	Non-PD/ or not all evaluated	No	PR
SD	Non-PD or not all evaluated	No	SD
Not all evaluated	Non-PD	No	Non-evaluable
PD	Any	Yes or No	PD
Any	PD*	Yes or No	PD
Any	Any	Yes	PD

*In exceptional circumstances, unequivocal progression in non-target lesions may be accepted as disease progression.

Subjects with a global deterioration of health status requiring discontinuation of treatment without objective evidence of disease progression at that time should be classified as having “symptomatic deterioration.” Every effort should be made to document the objective progression even after discontinuation of treatment.

In some circumstances, it may be difficult to distinguish residual disease from normal tissue. When the evaluation of complete response depends on this determination, it is recommended that the residual lesion be investigated (fine needle aspirate/biopsy) to confirm the complete response status.

9.8 Definitions for Response Evaluation – RECIST 1.1

9.8.1 First Documentation of Response

The time between initiation of therapy and first documentation of PR or CR.

9.8.2 Confirmation of Response

To be assigned a status of complete or partial response, changes in tumor measurements must be confirmed by repeat assessments performed no less than four weeks after the criteria for response are first met.

9.8.3 Objective Response Rate

The objective response rate is the proportion of all subjects with confirmed PR or CR according to RECIST 1.1, from the start of treatment until disease progression/recurrence (taking as reference for progressive disease the smallest measurements recorded since the start of treatment).

9.8.4 Progression Free Survival

A measurement from the date of treatment start until the criteria for disease progression is met as defined by RECIST 1.1 or death occurs. Subjects who have not progressed will be right-censored at the date of the last disease evaluation.

9.8.5 Overall Survival

Overall survival is defined by the date of treatment start to date of death from any cause.

9.9 Immune Related Response Criteria (irRC)

This study will evaluate concordance of the Immune Related Response Criteria (irRC) with RECIST 1.1. These response criteria were developed to overcome the variable and unusual patterns of response to immunotherapeutic agents, in particular, ipilimumab. The development of the guidelines was prompted by observations, mostly in subjects with metastatic melanoma, of initial disease progression followed by later response, late responses, and mixed responses with an overall decrease in tumor burden. See article in Clin Cancer Res 2009;15(23) December 1, 2009.

